Common adverse events

Overall, the safety and tolerability profile is similar to the GLP-1 RA class. Gastrointestinal AEs such as nausea, vomiting, and diarrhea were the most common AEs seen in the tirzepatide-treated participants.

Hypoglycemic events

In line with the ability of tirzepatide to lower blood glucose in a glucose-dependent manner, the overall incidence of clinically significant or severe hypoglycemia attributable to tirzepatide was low. The risk of clinically significant hypoglycemia or severe hypoglycemia was higher when tirzepatide was used in combination with insulin glargine or sulfonylurea, as has been observed with the GLP-1 RA class (Del Prato et al. 2021; Frías et al. 2021; Ludvik et al. 2021; Rosenstock et al. 2021; Dahl et al. 2022).

Tirzepatide once weekly versus dulaglutide once weekly

A 26-week Phase 2 study provided initial safety, tolerability, and efficacy data for tirzepatide 1 mg, 5 mg, 10 mg, and 15 mg in participants with T2D. Doses of 5 mg, 10 mg, and 15 mg of tirzepatide QW provided significantly greater reductions in HbA1c and body weight compared with dulaglutide 1.5 mg QW. The most common AEs, which were also dose dependent, were mild-to-moderate nausea, vomiting, and diarrhea (Frías et al. 2018).

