5.1. Inclusion Criteria

Participants are eligible to be included in the study only if all of the following criteria apply:

Age

1. Are 18 years old or of an acceptable age to provide informed consent according to local regulations, whichever is older.

Type of participant and disease characteristics

2. Have been diagnosed with T2D based on the World Health Organization classification or other locally applicable diagnostic standards.
3. Have HbA1c $\geq 7.0\%$ (≥ 53 mmol/mol) to $\leq 9.5\%$ (≤ 80 mmol/mol), as determined by the central laboratory at Visit 1.
4. Are currently on a stable dose of dulaglutide weekly (0.75 mg or 1.5 mg) for at least 6 months prior to Visit 1.
5. No treatment with OAM, or on a stable dose of up to 3 OAMs, which may include metformin, SGLT-2i, and/or sulfonylurea, for at least 3 months before Visit 1.

Weight

6. Have had stable body weight ($\pm 5\%$) during the 90 days preceding screening and agree to not initiate a diet and/or exercise program during the study with the intent of reducing body weight other than the lifestyle and dietary measures for diabetes treatment.
7. Have BMI ≥ 25 kg/m² at Visit 1.

Contraceptive/barrier requirements

8. Contraceptive use by participants should be consistent with local regulations regarding the methods of contraception for those participating in clinical studies.
 - Males may participate in this trial.
Please refer to Section 10.4 for additional guidance related to contraception.
 - WOCBP and women not of childbearing potential may participate in the study.
See Section 10.4 for definitions and additional requirements related to contraception.

Informed consent

9. Capable of giving signed informed consent as described in Section 10.1.3, Appendix 1, which includes compliance with the requirements and restrictions listed in the ICF and in this protocol.

Other inclusions

10. Are reliable and willing to make themselves available for the duration of the study and are willing and able to follow study procedures as required, including, but not limited to
 - self-injecting intervention or injection by a caregiver when applicable
 - willing to be assigned to a different injectable at randomization
 - taking provided study interventions as directed
 - maintaining an eDiary, and
 - completing electronic patient-reported questionnaires.

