27. Have a history of an active or untreated malignancy or are in remission from a clinically significant malignancy for less than 5 years.

Exceptions:

- a. basal or squamous cell skin cancer
- b. *in situ* carcinomas of the cervix, and
- c. *in situ* or Grade 1 (for example, Gleason 6 or lower) prostate cancer.

28. Have a history of any other condition such as known drug or alcohol abuse, or psychiatric disorder that, in the opinion of the investigator, may preclude the participant from following and completing the protocol.
29. Have any chronic hematological condition that may interfere with HbA1c measurement such as hemolytic anemias and sickle cell disease.
30. Female participants who are pregnant or breast feeding or intending to become pregnant during the course of the study.
31. Have a history of an underlying disease, presence of an underlying disease such as active SARS-CoV-2 infection, or surgical, physical, or medical condition that, in the opinion of the investigator, would potentially affect participant safety within the study or interfere with the interpretation of data.

Prior/concomitant therapy

32. Have been treated with insulin prior to screening.
Exception: use of insulin for gestational diabetes or short-term use (<14 days) for acute conditions, such as acute illness, hospitalization, or elective surgery.
33. Have a history of reduction of dose of dulaglutide weekly, due to intolerance, without successful reescalation, any time prior to Visit 1.
34. Have within 90 days prior to screening received treatment with medications intended to promote weight loss. This includes prescribed or over-the-counter or alternative remedies. See Section 6.8.3 for list of prohibited medications.
35. Are receiving chronic (>14 days) systemic glucocorticoid therapy or have received such therapy within 1 month of Visit 1 or between Visits 1 and 3.
Exceptions: topical, intraocular, intranasal, or inhaled preparations.

Prior/concurrent clinical study experience

36. Are currently enrolled in any other clinical study involving an investigational product or any other type of medical research judged not to be scientifically or medically compatible with this study.

37. Have participated, within the last 30 days, in a clinical study involving an investigational product. If the previous investigational product has a long half-life, 5 half-lives or 30 days (whichever is longer), should have passed prior to screening.

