6.3. Measures to Minimize Bias: Randomization and Blinding

Randomization

All participants will be centrally assigned through block randomization with a block size of 2 using an IWRS. Before the study is initiated, the login information and directions for the IWRS will be provided to each site.

Participants will be randomly assigned in a 1:1 ratio to tirzepatide or dose escalation of dulaglutide.

Participants will be stratified based on

- starting dulaglutide dose at Screening (0.75 mg, 1.5 mg)
- region (NA, EU)
- number of OAM (0-1 or 2-3), and
- HbA1c ($\leq 8.5\%$ or $> 8.5\%$).

Blinding

This is an open-label study.

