**Level 3 Severe**

A severe hypoglycemic event is characterized by altered mental or physical status requiring assistance of another person to actively administer carbohydrate, glucagon, or other resuscitative actions for the treatment of hypoglycemia.

The determination of an episode of severe hypoglycemia is made by the investigator based on the medical need of the participant to have required assistance and is not predicated on the report of a participant simply having received assistance.

Examples of severe hypoglycemia in adults are

- altered mental status and the inability to assist in their own care
- semiconscious or unconscious, or
- coma with or without seizures.

**Severe hypoglycemia:** A severe hypoglycemic event is characterized by altered mental or physical status requiring assistance of another person to actively administer carbohydrate, glucagon, or other resuscitative actions for the treatment of hypoglycemia.

**Nocturnal hypoglycemia:** Nocturnal hypoglycemia is a hypoglycemia event, including severe hypoglycemia, which **occurs at night** and presumably during sleep.

To avoid duplicate reporting, all consecutive BG values occurring within a 1-hour period may be considered to be a single hypoglycemic event and the one with the lowest BG value can be selected to be the representative. If two records with the same lowest values within a hour, the earlier occurrence will be selected.

Statistical summaries and analyses will exclude hypoglycemic events occurring after initiation of a new antihyperglycemic therapy. For severe hypoglycemia and level 2 hypoglycemia incidence as well as rate per patient year of exposure will be provided by treatment at specified time intervals. The incidence of hypoglycemic event will be analyzed using logistic regression with treatment, number of background OAMs (0 to 1, 2 to 3), dulaglutide dose at screening, baseline HbA1c category ( $\leq 8.5\%$ ,  $> 8.5\%$ ), and region as fixed effects. The rate of hypoglycemic episodes per patient year may be analyzed using a generalized linear MMRM assuming the number of hypoglycemic episodes follows a negative binomial distribution with the mean modeled using region, number of background OAMs (0 to 1, 2 to 3), dulaglutide dose at screening, baseline HbA1c category ( $\leq 8.5\%$ ,  $> 8.5\%$ ), and treatment as fixed effects if data warrants. The logarithm of years in specified time interval will be adjusted as an offset to account for possible unequal

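### The hypoglycemia models adjust for the number of oral agents but not for baseline sulfonylurea use, so a chance imbalance in that drug is only partly accounted for

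*SAP*

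**What the plan says.** SAP 4.6.2.1 plans two models for hypoglycemia. For incidence it states: "The incidence of hypoglycemic event will be analyzed using logistic regression with treatment, number of background OAMs (0 to 1, 2 to 3"; the remaining terms are screening dulaglutide dose, baseline HbA1c category and region. For the rate it gives a negative binomial model, to be used if the data allow, "with the mean modeled using region, number of background OAMs (0 to 1, 2 to 3), dulaglutide dose at screening", baseline HbA1c category and treatment. Neither has a term for sulfonylurea. With fewer than 10 events, a listing replaces the analysis.

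Protocol 2.2 reports that the risk was "higher when tirzepatide was used in combination with insulin glargine or sulfonylurea". Of these two drugs, only sulfonylurea can be background treatment here. Exclusion 32 in Protocol 5.2 bars people who "Have been treated with insulin prior to screening", apart from gestational or short-term use. Inclusion 5 in Protocol 5.1 admits people "on a stable dose of up to 3 OAMs, which may include metformin, SGLT-2i, and/or sulfonylurea".

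The oral-agent stratification factor in Protocol 6.3 is a count, "number of OAM (0-1 or 2-3), and" the SAP repeats it in section 1.2. Drug class is not a factor.

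**The concern.** The count does not identify the drug that matters. The 2-3 level pools metformin plus SGLT-2i with metformin plus sulfonylurea, and sulfonylurea alone falls in the 0-1 level. Protocol 6.8.5 itself treats sulfonylurea users separately when it describes background changes after hypoglycemia, so the distinction is already material within the plan.

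No other section fills the gap. The characteristics named in SAP Appendix 1 and the medications of interest in SAP Appendix 3 do not include sulfonylurea (the Appendix 1 list is open-ended, but it makes no commitment). The subgroups in SAP 4.7.1 cover HbA1c and weight only, and none is by sulfonylurea use. Hypoglycemia is a safety topic of special interest (Protocol 8.3.3) and one component of the composite secondary endpoint, whose models in SAP 4.4.2.2 also lack the term.

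At stake is how a difference in hypoglycemia between arms is read. If sulfonylurea use happened to be uneven, the planned output would neither adjust for it nor necessarily show it.

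**Working it through.** **The plan's own figures.** The documents state no figure for hypoglycemia. The only design input needed is about 250 participants randomized 1:1, so 125 per arm (SAP 5). The HbA1c power statements there are met (125 per arm gives 94% for 0.58/1.3 and 99% for 0.60/1.1), but they do not bear on this point.

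**Assumed inputs.** The documents give neither the proportion on sulfonylurea nor any event risk, so both are varied below.

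**Step 1: how large an imbalance, and what it does to an unadjusted ratio.** Under simple randomization with a proportion p on sulfonylurea, the SD of the between-arm difference is sqrt(2p(1 - p)/125). For p = 0.25 this is sqrt(0.375/125) = 0.055, or 5.5 points. With sulfonylurea risk ratio R, an imbalance d and no treatment effect, the apparent risk ratio is [1 + (p + d/2)(R - 1)] / [1 + (p - d/2)(R - 1)]. For p = 0.25, R = 4 and d = 1.96 SD = 0.107, this is 1.911/1.589 = 1.203.

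| Use | SD (points) | R = 2: 1 SD / 1.96 SD | R = 4: 1 SD / 1.96 SD | R = 6: 1 SD / 1.96 SD |
|---|---|---|---|---|
| 10% | 3.8 | 1.035 / 1.070 | 1.092 / 1.188 | 1.135 / 1.283 |
| 25% | 5.5 | 1.045 / 1.090 | 1.099 / 1.203 | 1.130 / 1.271 |
| 40% | 6.2 | 1.045 / 1.091 | 1.088 / 1.181 | 1.109 / 1.225 |

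This ignores stratification on, and adjustment for, the number of oral agents, so it is a rough upper guide.

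**Step 2: the planned logistic model itself.** Trials of 250 were simulated with blocks of 2 within the four stratification factors and no treatment effect, 6,000 per scenario. Sulfonylurea was more common in the 2-3 stratum. The SAP's logistic model was fitted with and without baseline sulfonylurea whenever at least 10 participants had an event. Paired entries are planned model / with the added term. The imbalances shown are an excess of users in the tirzepatide arm.

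| Use | Risk without sulfonylurea | Sulfonylurea OR | Type I error, all trials | Median OR, 3-7 points | Median OR, 7-13 points | Rejection, 7-13 points | Mean SE of log OR |
|---|---|---|---|---|---|---|---|
| 25% | 2% | 5 | 0.038 / 0.043 | 1.02 / 0.96 | 1.21 / 1.07 | 0.048 / 0.053 | 0.633 / 0.650 |
| 25% | 5% | 4 | 0.043 / 0.044 | 1.10 / 0.99 | 1.16 / 0.98 | 0.054 / 0.042 | 0.490 / 0.503 |
| 25% | 5% | 8 | 0.050 / 0.048 | 1.13 / 1.00 | 1.24 / 0.97 | 0.082 / 0.056 | 0.422 / 0.450 |
| 35% | 5% | 4 | 0.042 / 0.049 | 1.07 / 0.99 | 1.15 / 0.98 | 0.060 / 0.055 | 0.457 / 0.468 |
| 11% | 5% | 4 | 0.041 / 0.046 | 1.11 / 0.99 | 1.30 / 1.04 | 0.070 / 0.050 | 0.546 / 0.561 |

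The mean log OR is near 0 for both models in every scenario. Stratifying on the number of agents lowers the SD of the imbalance at 25% use only from 5.5 to 4.8-4.9 points.

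**Step 3: how often, and how large against noise.** An excess of 7-13 points in the tirzepatide arm occurred in 201/5,685 = 3.5% to 469/5,989 = 7.8% of fitted trials, and the opposite excess is equally likely by symmetry. The shift is ln(1.15)/0.457 = 0.31 standard errors in the fourth row and ln(1.24)/0.422 = 0.51 in the third; the other rows lie between about 0.3 and 0.5. A 95% interval extends by a factor of exp(1.96 x 0.42) = 2.3 to exp(1.96 x 0.63) = 3.4 on either side of the estimate.

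**Step 4: whether the model runs.** In the first scenario, 51% of trials had fewer than 10 participants with an event. The SAP counts events, not participants, so this is an upper guide to how often a listing would replace the model.

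**The case against.** The planned model is coherent: it adjusts for all four stratification factors. Randomization makes the comparison valid with or without sulfonylurea, and the confidence interval already allows for chance imbalance on average. The analysis lies outside the multiplicity hierarchy in SAP 2.1, so no confirmatory conclusion depends on it. Events may be too few to fit the model, and a further term makes sparse data worse. Sulfonylurea use and its effect on risk are assumed. The effect may be dampened because Protocol 6.8.5 lets the dose be reduced, and because Protocol 5.1 and 5.2 require a screening HbA1c of at least 7.0% and exclude recent severe hypoglycemia. Finally, SAP 4.1 permits further exploratory analyses without amendment.

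All but the last of these stand, and they limit the point. The last does not answer it: a sulfonylurea breakdown added after an imbalance has been seen would look data-driven.

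A reader might also infer that adding the term would tighten the estimate. For the logistic model it does not: the standard error of the log odds ratio rose in all five scenarios. In one further scenario with a true odds ratio of 2.5, rejection was 0.592 for the planned model and 0.607 with the term, so power changed little.

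**Conclusion.** The omission is real in both models, and the number of agents stands in for sulfonylurea only in part. In a trial that happens to have 7 to 13 points more users in one arm, the planned logistic model gives a median odds ratio of about 1.15 to 1.30 where none exists, and the added term removes most of that. This rests on assumed use of about 11% to 35%, risk without sulfonylurea of 2% to 5%, and a sulfonylurea odds ratio of 4 to 8. Only the logistic model was simulated.

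It would be tempting to conclude that the comparison is biased or its error rate inflated. That does not follow: treatment is randomized, the simulated type I error is 0.050 or lower, and the conditional shift is about 0.3 to 0.5 standard errors. Nor do the documents call sulfonylurea the strongest predictor. Protocol 2.2 says only that risk was higher, and it names insulin glargine as well. This is an inexpensive improvement to a safety analysis, not a flaw that invalidates it.

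**What to change.** In SAP 4.6.2.1:

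1. Keep the number of oral agents, because it is a stratification factor, and add baseline sulfonylurea use (yes/no, at randomization) to the logistic and negative binomial models. At minimum, prespecify this as a sensitivity analysis.
2. Tabulate baseline sulfonylurea use by arm.
3. Report the incidence and rate of level 2 and severe hypoglycemia by arm and baseline sulfonylurea use.
4. Show sulfonylurea status in the listing used when there are fewer than 10 events.

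The data are already collected: Protocol 1.3 schedules concomitant medications at every visit. Protocol 9.3.5.1 names no covariates for hypoglycemia, so the change conflicts with nothing there.

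The cost is one more parameter (seven instead of six in the logistic model) when events may number as few as 10, with no gain in the logistic standard error. The term must be baseline use, since later use can change in response to hypoglycemia. It does not correct for sulfonylurea changes after randomization under Protocol 6.8.5, which in an open-label trial could differ between arms.

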#### **4.6.2.2. Severe Persistent Hyperglycemia**

A summary statistic of initiation of rescue therapy in response to severe, persistent hyperglycemia will be provided by treatment. A listing of participants who initiated rescue therapy will be provided.

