6.1.4. Rescue Therapy

If a participant develops severe, persistent hyperglycemia after randomization, an additional antihyperglycemic medication may be medically indicated after investigator assessment.

Investigators will be trained on the application of criteria for deciding when and how to intervene with participants who do not reach glycemic targets.

First, investigators should confirm participant compliance with the assigned intervention and that they do not have an acute condition causing severe, persistent hyperglycemia.

Conditions for rescue therapy

The criteria for rescue therapy will be based on either FBG or HbA1c as described below.

FBG conditions

This table describes FBG conditions for rescue therapy.

If any of the FBG values exceed the limits outlined below for 2 consecutive weeks and no intercurrent cause of the hyperglycemia can be identified, participants should be treated with rescue medication as an add-on to randomly assigned treatment.

If a participant has persistently elevated FBG defined as...	during this time...	then...
FBG >270 mg/dL (>15.0 mmol/L)	from baseline (V3) to Week 8	participants should be treated with rescue medication as an add-on to randomly assigned treatment.
FBG >240 mg/dL (>13.3 mmol/L)	from Week 9 to Week 16	
FBG >200 mg/dL (>11.1 mmol/L)	Any time after Week 16	

Abbreviation: FBG = fasting blood glucose.

HbA1c conditions

This table describes HbA1c conditions for rescue therapy.

If a participant has an...	during this time...	then...
HbA1c ≥8.5% (≥64 mmol/mol)	any time after Week 24	participants should be treated with rescue medication as an add-on to randomly assigned treatment.

Abbreviation: HbA1c = glycated hemoglobin.

Allowed rescue treatments

The choice of rescue treatment for persistent hyperglycemia will be at the discretion of the investigator. Investigators should follow current published standards of care from the American Diabetes Association and/or the consensus report by the American Diabetes Association and the European Association for the Study of Diabetes (Buse et al. 2020; ADA 2022).

GLP-1 RAs, DPP-4 inhibitors, and pramlintide are not allowed as rescue therapy.

Additionally, tirzepatide is not allowed as rescue therapy for the dulaglutide group.

Rescue therapy will be continued and adjusted per the investigator's discretion.

Rescue therapy may not include modifying the tirzepatide or dulaglutide dose.

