8.3.3.7. Severe, Persistent Hyperglycemia

Severe, persistent hyperglycemia will be assessed during the study to determine the risk of extreme imbalance in glycemic control.

Investigators will be trained on the application of criteria for deciding when and how to intervene with participants who do not reach glycemic targets. An additional therapeutic intervention should be considered in participants who develop severe, persistent hyperglycemia after randomization. Participants will be treated with rescue medication as an add-on to randomly assigned treatment, and participants will continue to follow the protocol-specified visit schedule as described in Section 6.1.4.

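### SAP 4.6.2.2 counts severe, persistent hyperglycemia only by rescue starts, so participants who meet the protocol's numeric criteria without being rescued go uncounted

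*SAP*

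**What the plan says.** Protocol 8.3.3 lists severe, persistent hyperglycemia among the safety topics of special interest, and 8.3.3.7 gives the purpose: "Severe, persistent hyperglycemia will be assessed during the study to determine the risk of extreme imbalance in glycemic control". Protocol 6.8.5 treats it as something whose criteria a participant can meet.

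The numeric criteria are in Protocol 6.1.4. The FBG limit falls by period: above 270 mg/dL to Week 8, above 240 mg/dL in Weeks 9 to 16, and above 200 mg/dL after that. It must be exceeded for 2 consecutive weeks with no intercurrent cause found. The HbA1c limit applies after Week 24 and is printed in two units as "HbA1c ≥8.5% (≥64 mmol/mol".

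On what follows, the wording varies in strength. Protocol 6.1.4 opens with "an additional antihyperglycemic medication may be medically indicated after investigator assessment", and 8.3.3.7 has "An additional therapeutic intervention should be considered in participants who develop severe, persistent hyperglycemia after randomization". Once the criteria are met, however, 6.1.4 says that "participants should be treated with rescue medication as an add-on to randomly assigned treatment".

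SAP 4.6.2.2 plans two outputs, the summary "A summary statistic of initiation of rescue therapy in response to severe, persistent hyperglycemia will be provided by treatment" and "A listing of participants who initiated rescue therapy will be provided". SAP 6.3 (Appendix 3) has one line for rescue therapy and a separate line for antihyperglycemic drugs started after study treatment is stopped.

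**The concern.** The SAP reports the response to the event and not the event. Whether a participant is counted depends on a site decision made with knowledge of the arm. The two coincide only if everyone who meets the criteria is rescued and can still be rescued.

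This also departs from the SAP's own practice. Hypoglycemia, pancreatic enzymes, calcitonin and liver enzymes are all classified by measured thresholds.

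At stake is the description of one safety topic, and a view of how rescue was applied. Starting rescue is one of the events that cuts data from the Efficacy Analysis Set (SAP 3). Without a table of criteria met against rescue started, a reader cannot see whether that cut was applied evenly across arms.

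**Working it through.** **1. Who can meet the criteria and not be counted**

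- *Not rescued.* SAP 4.6.2.2 counts and lists only participants who started rescue. Anyone who meets the limits in Protocol 6.1.4 without rescue is absent from both outputs. This follows directly from the text.
- *First met at Week 40.* The HbA1c rule applies after Week 24. The scheduled treatment-period HbA1c visits left are Weeks 32 and 40 (Protocol 1.3). A participant first at or above the limit at Week 40 has finished the treatment period, so rescue as an add-on to assigned treatment can no longer begin. No investigator bias is needed for this omission.
- *Off study drug.* Protocol 6.1.4 defines rescue as an add-on to assigned treatment. Participants who stop for intolerance start another antihyperglycemic drug (6.5.2), which 6.8.4 lists as a separate circumstance. SAP 6.3 gives these starts their own line, not tied to glucose. They are probably outside the rescue summary, but this is an inference.
- *Unclear.* Protocol 6.8.5 lets the sulfonylurea dose rise when the criteria are met. The SAP does not say whether that counts as initiating rescue.

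**2. Is the gap filled elsewhere?** SAP 4.3 summarizes HbA1c by treatment and visit, and a hyperglycemia adverse event would appear in the adverse event tables if reported. Neither applies the 6.1.4 criteria.

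**3. Size.** The documents give no rate of criteria met and no rate of rescue, so there is no plan figure to reproduce. The mechanism can only be illustrated. Let N = 125 per arm (250 randomized 1:1), p = the share meeting the criteria, and r = the share of those who are rescued. The expected number counted is N × p × r. All values of p and r below are assumptions.

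| p, tirzepatide / dulaglutide | r, tirzepatide / dulaglutide | Meet criteria | Counted | Dulaglutide-to-tirzepatide ratio counted (true) |
|---|---|---|---|---|
| 10% / 10% | 80% / 80% | 12.5 / 12.5 | 10.0 / 10.0 | 1.0 (1.0) |
| 10% / 10% | 50% / 50% | 12.5 / 12.5 | 6.25 / 6.25 | 1.0 (1.0) |
| 10% / 10% | 40% / 80% | 12.5 / 12.5 | 5.0 / 10.0 | 2.0 (1.0) |
| 5% / 10% | 80% / 40% | 6.25 / 12.5 | 5.0 / 5.0 | 1.0 (2.0) |

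Equal rescue shares lower the counts and leave the ratio alone. Unequal shares can create a difference or hide one.

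**4. Can a count be made from collected data?** Participants are trained to measure FBG at least twice a week, and the meter transmits to the eDiary (Protocol 8.1.2.1). HbA1c is a central laboratory value (8.1.1). The numeric limits can be applied to these data. The compliance check and the search for an intercurrent cause cannot. At the minimum frequency, 2 weeks hold only 2 × 2 = 4 readings, and no rule says how many must exceed the limit.

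**5. HbA1c units.** Protocol 5.1 pairs 7.0% with 53 mmol/mol and 9.5% with 80 mmol/mol. Assuming linearity:

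- slope = (80 − 53) / (9.5 − 7.0) = 10.8 mmol/mol per percentage point
- 8.5% corresponds to 53 + 1.5 × 10.8 = 69.2 mmol/mol
- 64 mmol/mol corresponds to 7.0 + (64 − 53) / 10.8 = 8.02%

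Allowing 0.5 mmol/mol of rounding in each anchor gives 68.7 to 69.7 mmol/mol and 7.97 to 8.06%. Rounding does not explain the pair 8.5% and 64 mmol/mol.

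**The case against.** The best defense is that rescue is triggered by criteria and is not a free choice. Protocol 6.1.4 sets numeric limits and says participants who meet them should be treated, 8.3.3.7 says they will be treated, and investigators are trained on the rules. Protocol 8.3.3.7 itself describes the topic through rescue, and Protocol 9.3.5 plans no hyperglycemia analysis, so the SAP drops nothing that the protocol promised. Rescue is summarized by arm, and the Full Analysis Set keeps data after rescue, so the treatment-regimen result does not depend on the rescue cut. All of this stands. It limits the undercount to failures to follow the rescue instruction, late first crossings and, probably, participants off drug.

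A reader might infer more than the documents support:

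- *That open-label rescue biases the comparison by a known amount or in a known direction.* No passage supports any particular split of rescue between arms. Nor can scheduled escalation drive it under the HbA1c rule: by the fixed schedule in Protocol 6.1.1, tirzepatide reaches 15 mg at Week 20 and dulaglutide reaches its top dose sooner, both before the rule applies. Delayed or repeated escalation could be an exception.
- *That participants off study drug are excluded.* The SAP never says so, and the Safety Analysis Set keeps data regardless of adherence.
- *That the event itself can be derived from glucose data.* It cannot, because compliance and intercurrent cause need investigator judgment. A threshold count is a broader event.
- *That nothing shows how rescue was used.* Only the cross-table of criteria met by rescue started is missing.

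**Conclusion.** The point holds as a gap in safety reporting. SAP 4.6.2.2 measures the topic only through rescue, and no other SAP section counts participants who met the numeric criteria. Two omissions are certain from the text: those who meet the criteria without rescue, and those first meeting the HbA1c criterion at Week 40. Omission of participants off study drug is probable.

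The size is unknown. It depends on site adherence to the rescue instruction, for which the documents give no figure, so neither the undercount nor any arm bias can be computed. The illustrative counts rest wholly on assumed rates. No hypothesis test or controlled endpoint is touched. This is a cheap improvement and not a threat to the trial's main conclusions.

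**What to change.** In SAP 4.6.2.2, keep the rescue summary and listing and add the following:

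1. By arm on the Safety Analysis Set, a descriptive count of participants with *numeric FBG or HbA1c criteria met*, from eDiary and central laboratory data, on or off study drug.
2. A cross-table of that count by rescue started (yes or no).
3. A label or footnote saying that the count reflects numeric limits only, because compliance and intercurrent cause are not assessed.
4. A rule for the 2-consecutive-week FBG condition when readings may come only twice a week, and a statement on whether a sulfonylurea increase counts as rescue.

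Before programming, the sponsor must reconcile the two units of the HbA1c limit in Protocol 6.1.4 with the pairs in 5.1. This review does not say which value is intended.

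The cost is SAP wording and modest programming, with no new data collection. The drawback is a count broader than the clinically confirmed event, which the label makes plain.
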